7.2 Recruitment and screening

Patients who are admitted to the hospital for treatment of confirmed COVID-19 infection will be screened after results from history (symptom onset) and routine investigations (including a CT scan or X-ray of the chest) are available. Patients that at least fulfil the age, CT/X-ray chest criteria, positive SARS-CoV-2 PCR and reason for admission will be approached by a study doctor to explain the study, verify inclusion/exclusion criteria and obtain informed consent. Participants will have at least two hours and the opportunity to ask questions in order to decide on their participation

7.3 Assignment to study groups

Following study enrolment, an investigator or study nurse will determine treatment allocation via the electronic data management system, stratified according to the study site. Subsequently, conestat alfa will be supplied by the local pharmacy to the respective ward and can then be prepared by a regular ward nurse for administration in the active treatment group. The pharmacy of the University Hospital Basel will distribute conestat alfa within Switzerland. The Sponsor-Investigator will organize the distribution of the drug to non-Swiss sites in collaboration with the drug manufacturer Pharming Technologies B.V.

7.4 Criteria for withdrawal / discontinuation of participants

Subjects may voluntarily withdraw from study participation at any time without having to provide a reason. Subjects may be withdrawn because of the appearance of a new health condition requiring care or medications prohibited by the protocol, unacceptable adverse event, refusal to continue treatment, or at the Investigator's discretion if it is in the subject's best interest.

A subject who withdraws informed consent before randomization or who develops a violation of the selection criteria before randomization is defined as a screening failure. No follow-up of screening failures will be performed.

Participants who withdraw informed consent, who do not fulfil inclusion/exclusion criteria after obtaining informed consent AND have not received any study medication will be withdrawn from the study.

Participants who experience a type I allergic reaction after any dose of study medication will be discontinued from further study interventions. Withdrawn or discontinued participants will not be replaced. Follow-up for all patient groups will be explained in Section 9.2.5.

8. STUDY INTERVENTION

8.1 Identity of Investigational Products (treatment / medical device)

8.1.1 Experimental Intervention (treatment)

Conestat alfa (Ruconest®) will be supplied by the production company Pharming Technologies, B.V., the Netherlands. Conestat alfa is a recombinant analogue of human C1INH for intravenous injection. The primary and secondary structures of the molecule and target protease selectivity are consistent with those of plasma-derived C1INH. Conestat alfa is purified from the milk of transgenic rabbits, and supplied as a sterile, preservative-free, white/off-white lyophilized powder for reconstitution for injection. Conestat alfa contains less than 0.002% of rabbit-related impurities. One international unit (U) of Conestat alfa activity is defined as the equivalent of C1INH activity present in 1 mL of pooled normal plasma. Each vial of Conestat alfa contains 2100 U of Conestat alfa, 937 mg of sucrose, 83.3 mg of sodium citrate dihydrate and 1.0 mg of citric acid monohydrate. After reconstitution with 14 mL of sterile water for injection, each vial of Conestat alfa contains 150 U of Conestat alfa per 1 mL in a 20 mM sodium citrate buffer with a pH of 6.8. Conestat does not contain preservatives and each vial is for single use only. After randomization, a study nurse will open the respective sealed boxes, will reconstitute the respective number of conestat alfa vials and prepare the study medication for the intervention group. The control group will not receive any study medication. Conestat alfa is for intravenous use only. The reconstituted solution is administered as a slow intravenous injection over approximately ten minutes. Recommended doses of Conestat alfa for the treatment of an acute angioedema attack are 50 U/kg if body weight <84kg and 4200 U if >84kg. A second dose may be administered at the same recommended dose level within a 24 hour period. The experimental intervention in our study does deviate from the Summary of Product characteristics regarding dosing of the licensed product. In addition, we will not use the product according to the licensed indication (FDA and EMA). A market batch will be used for the study.

8.1.2 Control Intervention (standard/routine/comparator treatment / medical device)

Participants in the control arm will receive SOC treatment according to local guidelines.

8.1.3 Packaging, Labelling and Supply (re-supply)

The investigational product (conestat alfa) is supplied in single-use 25ml glass vials with a stopper (siliconized chlorobutyl rubber) and a flip-off seal (aluminium and colored plastic). Each carton contains one single-use vial. Sufficient amounts of conestat alfa will be supplied by the manufacturer Pharming Technologies B.V. to the pharmacy of the University Hospital Basel prior to study commencement. Both the carton and the glass vial of conestat alfa are labelled as "Ruconest® 2100 U, powder for solution for injection, conestat alfa. For intravenous use only". One vial contains 2100 U of conestat alfa, corresponding to 2100 U/14 ml after reconstitution, or a concentration of 150 U/ml. The pharmacy of the University Hospital Basel will distribute the investigational product to study sites in Switzerland. The Sponsor-Investigator will organize the distribution of the drug to non-Swiss sites in collaboration with the drug manufacturer Pharming Technologies B.V.

8.1.4 Storage Conditions

Conestat alfa will be stored at 2-25°C at the pharmacy of the study sites (shelf life 48 months when stored at 2-25°C) in a dedicated, secure and temperature-monitored study room which will be inaccessible to unauthorized personnel. Drug accountability will be monitored according to ICH-GCP E6 (R2) Guideline for Good Clinical Practice. More details are described in the Study Pharmacy Manual.

8.2 Administration of experimental and control interventions

8.2.1 Experimental Intervention

Conestat alfa (Ruconest®) will be administered as slow (5 min for 4200 U dose and 10 min for 8400 U dose) intravenous injection via a peripheral or central intravenous line. A uniform dose of 8400 U (initial dose) and 4200 U (subsequent doses) was chosen irrespective of body weight. The licensed dosage for conestat alfa is weight-based (50 U/kg up to 84 kg and 4200 U for a bodyweight of \geq 84 kg). This is based on the aim to at least achieve a level of 0.7 U/ml C1INH in patients with hereditary angioedema (lower limit of normal of C1INH activity). Simulation studies have revealed that this aim is achievable with the licensed dosing⁴⁸. However, these simulations have also shown that C1INH levels will be lower

when using 50 U/kg compared to 4200 U in patients with a bodyweight < 84kg. As for the current trial the aim is not to correct underlying *absolute* C1INH deficiency (as in case of hereditary angioedema), but to ensure that a level of at least twice the serum concentration will be achieved in the vast majority of patients, we will use a fixed dose for all patients irrespective of body weight.

In patients with normal C1INH levels, the chosen dose will increase plasma C1-inhibitor activities by at least 100% (4200 U) and 200% (8400 U), respectively. To maximise efficacy conestat alfa will be administered repeatedly over 72 hours. Maximal volume of the injection is 28ml (4200 U) and 56ml (8400 U) per administration, respectively.

Repeated administration of conestat alfa was chosen for several reasons. First, hyperinflammation caused by SARS-CoV-2 is a phenomenon that may last for several days, and hence sustained inhibition of the CS and the KK system is required. Second, the elimination half-life of conestat alfa was determined at 2.5 hours³⁴. Third a decline of C1 inhibitor activity to pre-administration levels was demonstrated within four to six hours after administration of conestat alfa at a dose of 50 U/kg⁴⁹. Hence, in order to generate supra-physiological C1INH for the majority of time during a 72h interval, administration of a loading dose followed by repeated injections of conestat alfa was chosen.

Duration of exposure to Conestat alfa will be approximately 74 hours (up to 10 hours after the last dose administered 64 hours after the first dose). Participants will be followed in hospital for at least 12 hours after the last dose and via structured telephone interviews four weeks later.

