The clinical development program supporting safety of conestat alfa is based on a total number of 268 unique patients (up to Oct 2018). Those 268 patients received a combined total of almost 1600 administrations of conestat alfa.

The treatment emergent adverse events (TEAEs) that occurred with onset within 7 days of treatment with conestat alfa that were most frequently reported (observed in $\geq 3\%$ of patients treated with conestat alfa) were headache (11%), nausea, and diarrhea (3% each). There was no evidence of an increase in the percentages of patients with TEAEs or related TEAEs, or in the seriousness or severity of TEAEs, with increases in conestat alfa dose, treatment of a larger number of attacks, and/or treatment of a single attack with an additional dose.

The ADRs listed in the European SmPC are headache (common) and vertigo, paresthesia, throat irritation, diarrhea, nausea, abdominal discomfort, oral paresthesia, urticaria, and swelling (all uncommon). As described in the US prescribing information for conestat alfa, AEs of headache, sneezing, angioedema, erythema marginatum, skin burning sensation, back pain, C-reactive protein increased, fibrin D-dimer increased, vertigo, lipoma, nausea, and diarrhea occurred in $\geq 2\%$ of conestat alfa -treated patients. Note that AEs are listed in the US prescribing information regardless a causal relationship with conestat alfa.

The frequency of adverse reactions listed above is defined using the following convention:

- Very common ($\geq 1/10$),
- Common ($\geq 1/100$ to $< 1/10$),
- Uncommon ($\geq 1/1,000$ to $< 1/100$),
- Rare ($\geq 1/10,000$ to $< 1/1,000$),
- Very rare ($< 1/10,000$),

Specific antidotes against conestat alfa do not exist. In the unlikely event of an allergic reaction, standard treatment regimens indicated by the clinical situation (e.g. epinephrine, antihistamines, corticosteroids, etc.) will be administered.

The level of risk may evolve over time, during the study: consequently, a Data Safety Monitoring Board (DSMB) will monitor the safety of all patients, as well as the continuing validity and scientific merit of the study. Currently, one competing trial in COVID-19 patients (WHO Solidarity trial) is conducted at one study site (Basel).

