5.4 Safety Outcomes

The study will evaluate the safety of conestat alfa in the setting of COVID-19 infections if added to SOC compared to SOC treatment only by measuring the incidence of adverse events up to 4 weeks inclusion.

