⁴IMP will be administered during a 64 hour period (+/-4 hours). Trial medication will be stopped in participants that are discharged or transferred to another facility.

⁵Can be omitted if results are available from the same day.

⁶A pregnancy test will be performed in women who may become pregnant, are sexually active, and do not use adequate contraceptive measures.

⁷Collection of samples will be before 1st administration of study medication and subsequently at least 4 hours after the administration of study medication.

⁸Collection of samples will be before 1st administration, 10 (+/-5) minutes after the 1st administration (day 0) and before and 10 (+/-5) minutes after one administration on day 1.

⁹The worst value recorded on a given day will be documented.

¹⁰optional for other centers depending on their ability to collect, centrifuge, aliquot and store blood and urine samples at -80°C.

¹¹IL-6 will not be measured on day 1

* If the patient was already discharged before day 7, the assessment of the WHO ordinal scale will be conducted via a short telephone interview (Score 1 or 2).

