9.2.4 Assessment of safety outcomes

9.2.4.1 Adverse events

Participants will be followed for adverse events during 4 weeks after enrolment. After the end of clinical follow-up there is no requirement to actively collect AEs including death.

Adverse events and clinical course including death within 4 weeks will be assessed by a structured telephone interview after 4 weeks. If necessary, medical charts will be reviewed, discharge summaries will be or the patients' general practitioner will be contacted regarding specific follow-up information. Every effort will be made to contact the trial subject and obtain complete data for follow-up. Conditions that started before signing informed consent will be recorded as medical history. Conditions that started or deteriorated after signing informed consent will be documented as AE. Definition of AE and SAE will be found in Section 10.

All AEs will be assessed and documented by the investigators according to seriousness, intensity, causal relationship with study treatment, action taken with study treatment (e.g. withdrawal), specific treatment for AE and outcome. In addition, time of onset and AE duration will be recorded. Procedures are defined in Section 10. AEs will be recorded on the respective eCRF pages.

Participants will be asked about any new events/complaints during the admission and at 4 weeks.

In addition, participants are asked to report any new events including hospital admission to the study team.

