11.4.5 Safety analysis

The assessment of safety will be based mainly on the frequency of adverse events (AEs) that are treatment-emergent (TEAEs). Formal tests will not be conducted for differences in safety parameters between treatment groups.

The incidence of all treatment-emergent AEs will be tabulated after grouping by system organ class and preferred term. For each preferred term and summarized over each system organ class overall, the

table will present the absolute number and proportion (%) of patients in each treatment group in whom the event occurred. The incidence of all suspected-IMP-related AEs will be tabulated similarly. The incidence of all treatment-emergent AEs will also be tabulated by severity categories.

Safety will also be summarized with respect to vital signs as mean levels by visit and change from baseline. Abnormal observations on physical exams will be listed.

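### After discharge, adverse events are actively sought only once, at about week 4, so the recording of later, mainly non-serious events can differ between arms in either direction

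*Protocol*

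**What the plan says.** The safety outcome (section 5.4) compares conestat alfa plus SOC with SOC alone "by measuring the incidence of adverse events up to 4 weeks inclusion". Section 9.2.4.1 sets the same length of follow-up in both arms: "Participants will be followed for adverse events during 4 weeks after enrolment".

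The timing of active enquiry is also in section 9.2.4.1: "Participants will be asked about any new events/complaints during the admission and at 4 weeks". Section 9.3 agrees. AEs are assessed at Visits 2 to 6, Visit 5 applies only while the patient is admitted, and Visit 6 moves from day 14 to the day of discharge if that comes earlier. Visit 7 is the week-4 interview. Section 8.2.1 says of the period after dosing: "Participants will be followed in hospital for at least 12 hours after the last dose and via structured telephone interviews four weeks later".

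Two provisions add to this. Section 9.2.4.1 says "In addition, participants are asked to report any new events including hospital admission to the study team", and it allows charts, discharge summaries or the general practitioner to be consulted where necessary.

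The one other scheduled contact after discharge is for patients who left before day 7. The footnote in section 9.1 says "the assessment of the WHO ordinal scale will be conducted via a short telephone interview (Score 1 or 2"; no AE question is mentioned there or under Visit 5.

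For the analysis, section 11.4.5 says the "table will present the absolute number and proportion (%) of patients in each treatment group in whom the event occurred", without formal tests. Section 11.4.1 uses the Safety Population for all safety analyses and defines it as patients who received at least one dose of conestat alfa.

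**The concern.** Time under active AE enquiry equals time in hospital, plus one recall interview. Time in hospital is not a baseline quantity. Live discharge is part of the time-to-improvement endpoint (sections 4.3 and 5.2), and length of stay is an outcome of interest (section 5.3). If the drug shortens the stay, treated patients have fewer days on which somebody asks about events. If the stay on conestat alfa is longer, they have more.

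A crude proportion over four weeks makes no allowance for this. The comparison with SOC can therefore differ because of how events were looked for. Events that were never asked about and are forgotten by week 4 cannot be recovered by any later analysis, so the collection schedule itself matters and not only the tables. According to section 3.4 conestat alfa had not been assessed in COVID-19 patients beyond five compassionate-use cases, and describing its safety is a stated objective.

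**Working it through.** **Stated figure.** Nine doses every 8 hours put the last dose at 8 × 8 = 64 h. Adding 10 h gives 74 h, which reproduces the exposure stated in section 8.2.1. Adding 12 h gives a planned inpatient observation of 76 h, or 3.2 days. That is 3.2/28 = 11% of the four-week window. The protocol gives no AE rate for this population and no expected length of stay, so everything below is illustration.

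**Model 1: different recorded rates in and out of hospital.** Let *a* be the recorded AE rate per day in hospital, *b* the rate after discharge and *L* the days in hospital.

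- Recorded four-week incidence = 1 − exp(−[*aL* + *b*(28 − *L*)]).
- Masked rate ratio = [*aL*(SOC) + *b*(28 − *L*(SOC))] / [*aL*(active) + *b*(28 − *L*(active))].

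The assumed ranges are *a* 0.05 to 0.15, *b* 0.01 to 0.05, an SOC stay of 9 days and an active stay 1 to 3 days shorter. The last row adds an active stay 2 days longer. The rates are the same in both arms.

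| *a* | *b* | Active stay (days) | SOC exponent | Active exponent | SOC | Active | SOC − active (points) | Ratio |
|---|---|---|---|---|---|---|---|---|
| 0.05 | 0.05 | any | 1.40 | 1.40 | 75.3% | 75.3% | 0 | 1.00 |
| 0.10 | 0.05 | 8 | 0.90 + 0.95 = 1.85 | 0.80 + 1.00 = 1.80 | 84.3% | 83.5% | 0.8 | 1.03 |
| 0.10 | 0.01 | 7 | 0.90 + 0.19 = 1.09 | 0.70 + 0.21 = 0.91 | 66.4% | 59.7% | 6.6 | 1.20 |
| 0.15 | 0.01 | 6 | 1.35 + 0.19 = 1.54 | 0.90 + 0.22 = 1.12 | 78.6% | 67.4% | 11.2 | 1.38 |
| 0.10 | 0.01 | 11 | 1.09 | 1.10 + 0.17 = 1.27 | 66.4% | 71.9% | −5.5 | 0.86 |

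For shorter active stays the range is 0 to 11.2 points, with ratios from 1.00 to 1.38. It is zero where recording is equally good before and after discharge. A longer active stay reverses the sign.

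**Model 2: constant true hazard, partial capture after discharge.** Assume full capture in hospital and a share *s* of later events captured at week 4. The hidden hazard ratio is [*L*(SOC) + *s*(28 − *L*(SOC))] / [*L*(active) + *s*(28 − *L*(active))].

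- Stay 10 v 6 days, *s* = 0.3: (10 + 5.4)/(6 + 6.6) = 15.4/12.6 = 1.22.
- Stay 10 v 6 days, *s* = 0.8: (10 + 14.4)/(6 + 17.6) = 24.4/23.6 = 1.03.
- Stay 12 v 7 days, *s* = 0.3: (12 + 4.8)/(7 + 6.3) = 16.8/13.3 = 1.26.
- Stay 8 v 10 days, *s* = 0.3: (8 + 6)/(10 + 5.4) = 14/15.4 = 0.91.
- Any stay, *s* = 1: 28/28 = 1.00.

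As an example, take true four-week risks of 30% on SOC and 36% on conestat alfa (hazard ratio 1.25) with stays of 10 and 6 days. With *s* = 0.3 they are recorded as 17.8% and 18.2%, and the excess disappears. With *s* = 0.8 they are recorded as 26.7% and 31.3%, and most of it survives.

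**The case against.** The other side has several good points.

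- **The exposed period is already watched.** Dosing, the roughly 74 h of exposure and 12 h after the last dose are planned in hospital, and the stated half-life is 2.5 h. Acute reactions fall where AEs are actively sought. A reader might infer that drug reactions go unseen; the protocol does not support that.
- **Serious events have other routes.** Self-reporting, record retrieval and the week-4 interview should recover most deaths, readmissions and other serious events.
- **The direction is not fixed.** A reader might infer that the scheme makes the drug look safer. That needs both imperfect recall and a shorter active stay, and neither is given. The 12-hour rule is stated for the dosed arm and could lengthen its stay. Even so, section 7.1 requires every participant to be expected to stay three calendar days, and section 8.3 ends dosing at discharge, so the asymmetry is modest. Open-label reporting could also add AEs on conestat alfa.
- **There is a fixed window.** It is four weeks in both arms.
- **The reference rates are not a comparator.** Section 3.7 describes AEs "that occurred with onset within 7 days of treatment with conestat alfa that were most frequently reported". Nothing in the protocol plans to compare trial incidence with them, so the different window is no defect.
- **Part of the gap may be real.** Patients are sicker in hospital. If the drug shortens illness, fewer AEs is partly a true effect, which Model 1 cannot separate from detection.
- **Safety is descriptive and the trial is small.** At a recorded 60%, the 95% half-width for 80 v 40 patients is 1.96 × √(0.24 × (1/80 + 1/40)) = 18.6 points, more than the largest artefact above.

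All of this limits the point to later, mainly non-serious events and to an unknown size and sign. It does not remove it: the intensity of enquiry still depends on an outcome that follows randomisation, and imprecision is no reason to leave an avoidable difference in data collection.

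**Conclusion.** The point holds in a limited form. Active AE enquiry stops at discharge and resumes once, at about week 4. Treatment may affect discharge, so crude four-week proportions could hide or create a difference between arms in later, mainly non-serious AEs. The protocol does not show which way, or that the effect is large. Under the assumed rates and stays it runs from 0 to 11 points, with a masked rate ratio of 1.00 to 1.38 when the active stay is shorter, and it changes sign when that stay is longer. If week-4 recall is good (80% captured), the hidden ratio for a 10 v 6 day stay is only 1.03.

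This calls for a cheap improvement; it does not invalidate the safety assessment or justify replacing the four-week outcome. A more direct obstacle to the same comparison is the Safety Population in section 11.4.1, which taken literally leaves no SOC patients in a by-arm table.

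**What to change.** 1. **Visit 5 and the section 9.1 footnote:** add the structured AE questions to the existing call for patients discharged before day 7, covering discharge to day 7. Those still in hospital are already asked, so AEs to day 7 are then actively sought in every patient.
2. **Section 11.4.5:** add a by-arm AE table from randomisation to day 7, in all treated and all SOC patients, beside the four-week table. Randomisation is the usable start, because section 10.1.1 separates treatment-emergent events by first treatment, which SOC patients never receive. The four-week table remains the stated outcome and is split by in-hospital and post-discharge onset. Onset time is already recorded (section 9.2.4.1).
3. **Sections 11.4.1 and 5.4:** reconcile the Safety Population with the comparison against SOC, so that these tables can be produced.

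The cost is a few questions in a call that is already made, one extra table and one corrected definition. There are two downsides. Prompting will record somewhat more mild events in patients discharged early. Enquiry after day 7 stays unequal, so the four-week table should be read with that in mind.
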